### Primary Outcome Measures:

1. Change from baseline in Liver Enzyme Profile (Aspartate Aminotransferase [AST], Alanine Aminotransferase [ALT], and Gamma-Glutamyl Transferase [GGT]) at 3 and 6 months. Measured in units per liter (U/L) and reported as absolute and percentage change. Lower values indicate improved liver function.
2. Between-group difference in Liver Enzyme Profile (AST, ALT, GGT) at 3 and 6 months (Tocotrienol-Rich Fraction vs placebo). Measured in U/L. Lower values indicate improvement.
3. Change from baseline in Fatty Liver Index (FLI) at 3 and 6 months. Unitless score (range 0–100). Higher scores indicate greater hepatic steatosis (worse outcome). Reported as absolute and percentage change.
4. Between-group difference in Fatty Liver Index (FLI) at 3 and 6 months (Tocotrienol-Rich Fraction vs placebo). Range 0–100. Higher scores indicate worse steatosis.
5. Change from baseline in Liver Stiffness Measurement using Transient Elastography (FibroScan® score) at 3 and 6 months. Measured in kilopascals (kPa; typical range 2–75). Higher values indicate greater fibrosis. Reported as absolute and percentage change.
6. Between-group difference in Liver Stiffness Measurement (FibroScan® score) at 3 and 6 months (Tocotrienol-Rich Fraction vs placebo). Measured in kPa. Higher values indicate worse fibrosis.

\*Aspartate aminotransferase (AST) is usually used to detect liver damage. It is often ordered in conjunction with other liver enzymes, alanine aminotransferase (ALT) and gamma-glutamyl transpeptidase (GGT), or as part of a liver panel or comprehensive metabolic panel (CMP) to screen for and/or help diagnose liver disorders. The changes in these liver enzymes can also be used to monitor the compliance of patients toward alcohol abstinence.

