### **“Stopping rules” or “discontinuation criteria**

The participation of the trial subjects will be terminated if they cannot adhere to alcohol abstinence and cannot comply with the treatment regimes. Failure to adhere is a serious problem that not only affects the subjects but also the overall conduct and outcome of the research. They will also be stopped from participating in situations where the risks outweigh the anticipated benefits, in cases of severe allergic reactions or any adverse events that occurred in individual trial subjects. Subjects in these trials should be particularly closely monitored and should be withdrawn if they appear to be unduly distressed.

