### **Exclusion criteria:**

1. Severe alcoholic hepatitis defined as Maddrey's discriminant function  $>32$
2. Patients with other concomitant liver diseases:
  - a. Hepatitis B
  - b. Hepatitis C
  - c. Non-alcoholic fatty liver disease (NAFLD)
  - d. Autoimmune hepatitis (AIH)
  - e. Hereditary hemochromatosis
3. Patients who are obese (a BMI of  $30 \text{ kg/m}^2$  or more) and with metabolic syndromes
4. Patients with bleeding disorders and who have been on anticoagulant or antiaggregant treatments
5. Patients who have been on corticosteroid therapy or pentoxifylline for alcoholic hepatitis
6. Patients with hepatocellular carcinoma
7. Pregnant patients
8. Patients who are breastfeeding
9. Patients with Childs C liver cirrhosis
10. Patients who have pyridoxine allergy or history

11. Patients who are judged by investigator that participation of the study is difficult due to disease as follow; hepatic cirrhosis, Wilson's disease, malignant tumor, serious metabolic disease, severe renal disease, severe pulmonary disease, severe cardiovascular disease, severe nervous disease/psychiatric disorder, muscle disease and etc
12. Patients taking vitamin E, herbal supplements, or other investigational products within 90 days prior to the participation in the study.
13. Patients who have been taken any medications that could affect the treatment: hypoglycemic agents, colchicine, penicillamine, corticosteroids, ursodeoxycholic acid, pentoxifylline, long-term use of NSAIDs, statins, neuroleptics, anticonvulsant medications, high-dose acetaminophen( $\geq 2.5$ g/day)
14. Patients who have received treatment that may affect liver function within 1 month prior to the participation in the study
15. Patients who could not comply with alcohol abstinence.
16. Patient who considered ineligible for participation in the study as Investigator's judgment

**Note:** Patients enrolled in this study MUST abstain from alcohol consumption throughout the study period

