### **Withdrawal criteria**

During the course of the trial a subject may choose to withdraw early from the trial treatment at any time. This may happen for a number of reasons, including but not limited to:

- The occurrence of what the participant perceives as an intolerable adverse event (AE).
- Inability to comply with trial procedures
- Participant decision

Subjects may choose to stop their participation, and it will not affect their treatment at UKM-affiliated hospitals and clinics in any way. Without losing any of their rights as patients, they will not be penalised and can still continue with the standard treatment available and for follow-up visits at UKMMC. The data and samples already collected would not be used in the final study analysis and would be discarded.

In addition, we may discontinue a participant from the trial treatment at any time if we consider it necessary for any reason including, but not limited to:

- Pregnancy
- Ineligibility (either arising during the trial or retrospectively having been overlooked at screening)
- Significant non-compliance with treatment regimen or trial requirements
- An adverse event which requires discontinuation of the trial medication or results in inability to continue to comply with trial procedures

- Disease progression which requires discontinuation of the trial medication or results in inability to continue to comply with trial procedures

We have adjusted our sample size calculation for this study by considering the risk of dropout among the subjects. Hence, the withdrawn subjects will not be replaced while ensuring that the minimal sample size of this study is achieved. The type of withdrawal and reason for withdrawal will be recorded in the CRF. If the participant is withdrawn due to an adverse event, we will arrange them for follow-up visits at our clinic until the adverse event has resolved or stabilised.

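### Primary-outcome enzymes may also be used to judge abstinence, and non-abstinence can end participation, so the wording allows removal that depends on the outcome

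*Protocol*

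**What the plan says.** The first item under Primary Outcome Measures is "Change from baseline in Liver Enzyme Profile (Aspartate Aminotransferase [AST], Alanine Aminotransferase [ALT], and Gamma-Glutamyl Transferase [GGT]) at 3 and 6 months", and the second compares the same enzymes between groups. The footnote to that list adds a further use for them: "The changes in these liver enzymes can also be used to monitor the compliance of patients toward alcohol abstinence". It gives no threshold, timing or decision-maker.

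Three other places attach consequences to abstinence:

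- The note closing the exclusion criteria: "Patients enrolled in this study MUST abstain from alcohol consumption throughout the study period".
- The section on stopping rules: "The participation of the trial subjects will be terminated if they cannot adhere to alcohol abstinence and cannot comply with the treatment regimes".
- The list of investigator reasons for discontinuation under Withdrawal criteria: "Significant non-compliance with treatment regimen or trial requirements".

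Withdrawal criteria also says: "Hence, the withdrawn subjects will not be replaced while ensuring that the minimal sample size of this study is achieved".

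Other alcohol measures are named, but none is tied to termination. AUDIT is described under Screening. The abstract mentions alcohol questionnaires without a schedule. Treatment of Subjects refers to watching for withdrawal symptoms, with counselling or pharmacotherapy offered.

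**The concern.** A measure that decides who stays in a trial should not be the measure on which the trial is judged. Here the same enzyme change can do both. The protocol's second hypothesis is that tocotrienol normalises liver enzymes. If so, of two equally abstinent patients, the one on placebo is more likely to look non-abstinent. Blinding does not prevent this, because the enzyme value itself carries the treatment effect.

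The between-group comparison and the within-arm changes are both at stake, and both are listed as primary. A statistical analysis plan can choose how to handle missing visits, but it cannot restore visits that did not take place. The trial also has little slack: 13 per arm, 10 needed by its own calculation, and no replacement.

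**Working it through.** **1. The plan's own figure.** Sample Size Calculation gives means 12.82 and 3.86, SD 7.0, z-values 1.96 and 0.84. n = (2.80² × 2 × 7.0²) / 8.96² = 768.32 / 80.28 = 9.57, rounded up to 10. Allowing 20% loss, 10 / 0.8 = 12.5, rounded up to 13, so 26 in total. This reproduces and is not in dispute.

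**2. The route to removal.** Enzyme change may inform the abstinence judgement (footnote). Abstinence is mandatory (note to the exclusion criteria). Failure can end participation (stopping rules, withdrawal criteria). Nothing in the text bars enzyme values from that decision.

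**3. Illustration, removal and outcome at the same visit.** The protocol gives no enzyme means or SDs. Assumptions: the fatty liver index figures are borrowed and read as improvements, changes are normal, and a patient with improvement at or below a cut-off c is removed. With a = (μ − c)/7, the retained share is Φ(a) and the retained mean is μ + 7φ(a)/Φ(a).

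At c = 0:

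- Placebo: a = 0.551, retained 0.709 (29% removed), mean 3.86 + 3.38 = 7.24.
- Active: a = 1.831, retained 0.966 (3% removed), mean 12.82 + 0.54 = 13.36.
- Difference: 13.36 − 7.24 = 6.12 against 8.96, which is 32% less.

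At c = −3.5 the difference is 7.26 (19% less). At c = +3.5 it is 4.87 (46% less).

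**4. Illustration, month-3 values drive removal and month 6 is the outcome.** This is closer to how patients would leave. With equal SDs and an assumed month-3 to month-6 correlation ρ, the shift in each retained mean is multiplied by ρ. At c = 0 the difference is 8.96 − ρ(3.38 − 0.54):

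- ρ = 0.5: 7.54 (16% less).
- ρ = 0.8: 6.69 (25% less).

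Over c = −3.5 to +3.5 the range is 9% to 37%.

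**5. Dependence on placebo improvement.** In SD units, with placebo improvement m, true effect δ, h(x) = φ(x)/Φ(x) and c = 0 at the same visit, attenuation = [h(m) − h(m + δ)]/δ. For δ from 0.3 to 1.28:

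| m | Attenuation |
|---|---|
| 0.5 to 1.0 | 20% to 47% |
| 1.5 | (0.139 − 0.008)/1.28 = 10% to (0.139 − 0.082)/0.3 = 19% |
| 2.0 | (0.055 − 0.002)/1.28 = 4% to (0.055 − 0.029)/0.3 = 9% |

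The larger values of m are plausible, because Randomisation and Treatment expects these mild cases to resolve within months on abstinence alone.

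**6. Simulation check.** Standardised enzyme change, ρ of 0.5 to 0.8, worst 10% to 30% of month-3 changes removed (all assumed):

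| True effect (SD) | Removed, placebo | Removed, active | Observed month-6 effect (SD) |
|---|---|---|---|
| 0 | equal | equal | no bias |
| 0.5 | 14% to 39% | 6% to 21% | 0.30 to 0.43 |
| 1.0 | 17% to 46% | 3% to 14% | 0.61 to 0.87 |

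**7. Within-arm change.** With no true effect and both arms at the placebo value, step 3 gives a retained mean of 7.24 instead of 3.86 in each arm. The between-group difference is unaffected, but each within-arm fall is overstated.

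**The case against.** The strongest reply is that no rule removes anyone on enzymes. The footnote is permissive and says the enzymes can also serve as a monitor. The stopping-rule sentence does not mention enzymes and joins failure to abstain and failure to comply with treatment by an and, so read literally it needs both. Discontinuation for non-compliance is discretionary and must be significant, and the described response to difficulty with abstinence is support. All of this is correct, and it limits the point to what the wording allows. It does not close the route: the withdrawal list makes significant non-compliance with trial requirements sufficient by itself, abstinence is such a requirement, and an unwritten threshold leaves the matter to discretion. Questionnaires exist, but the text gives them no follow-up schedule. The flow chart could not be read.

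A reader might infer more, in three ways that the document does not support:

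- That removal on enzymes is planned. It is possible, not prescribed.
- That terminated patients' data are thrown away. The sentence "The data and samples already collected would not be used in the final study analysis and would be discarded" stands under voluntary withdrawal, and no separate rule covers patients terminated by the investigator. The point does not depend on it.
- That the effect will shrink by about a third. The 32% borrows another outcome's planning values and selects and measures at one visit. Even the direction is conditional: real drinking that raises enzymes, or removal unequal for other reasons, could change it. In these models no false positive arises between groups.

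**Conclusion.** The point holds as a defect of design wording that should be corrected. The protocol permits a primary outcome to inform the judgement that can end participation, and its text schedules no independent abstinence measure after screening. If tocotrienol lowers enzymes, removal on this basis would be heavier on placebo and, under the simple models above, would bias the between-group difference toward zero. If it has no effect and removal is equal, only the within-arm changes are distorted.

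The true size cannot be derived from the document. The illustrative values are 32% (same visit), 16% to 25% (month 3 to month 6, correlation 0.5 to 0.8) and 4% to 19% (same visit, placebo improvement of 1.5 to 2 SD). They rest on normality, the borrowed planning values or assumed standardised effects, and a cut-off that the protocol does not state. They show a mechanism and are not a forecast.

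**What to change.** - Remove the footnote sentence as a compliance rule, and state that AST, ALT and GGT changes are not used to classify abstinence. Say expressly that safety decisions on laboratory values, under the withdrawal and adverse event sections, are unaffected.
- Record abstinence at months 3 and 6 with the alcohol-consumption questionnaire already in the protocol, completed before that visit's enzyme results are seen.
- Reconcile the footnote, the stopping rules and the withdrawal criteria: which measure establishes non-abstinence, whether one failure or both are needed, and how terminated patients' data enter the analysis. What the clinical rule should be is for the investigators to decide.
- Whatever is decided about treatment, continue to collect month-3 and month-6 outcomes for randomised patients who consent, include them in the primary comparison, and record relapse as a variable.

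The cost is a wording change, a few minutes of questionnaire at two existing visits, and attendance by patients who would otherwise have left. The small downside is that self-report may miss some drinking, though it does so without selecting directly on the enzyme outcome.

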### Secondary Outcome Measures:

1. Change From Baseline in Plasma Cytokine Levels (Anti-inflammatory Effect of Tocotrienols) at baseline, 3 months, and 6 months.
  - Cytokines measured: Interleukin-6 (IL-6), Tumor Necrosis Factor-alpha (TNF- $\alpha$ ), Interleukin-1 beta (IL-1 $\beta$ ) in plasma; Method: Multiplex Enzyme-Linked Immunosorbent Assay (ELISA); Unit: picograms per milliliter (pg/mL); Typical range: IL-6 (0–50 pg/mL), TNF- $\alpha$  (0–100 pg/mL), IL-1 $\beta$  (0–50 pg/mL); Higher values indicate greater inflammation (worse outcome).

2. Change From Baseline in Metabolic Profile (Fasting Blood Glucose [FBG] and Lipid Panel) at baseline, 3 months, and 6 months.

•Parameters measured: FBG, total cholesterol (TC), low-density lipoprotein cholesterol (LDL-C), high-density lipoprotein cholesterol (HDL-C), and triglycerides (TG); Unit: milligrams per deciliter (mg/dL); Typical ranges: Fasting glucose (70–100 mg/dL), TC (125–200 mg/dL), LDL-C (0–130 mg/dL), HDL-C (40–60 mg/dL), TG (0–150 mg/dL); Higher values indicate worse metabolic profile.

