## **HYPOTHESIS**

1. TRF reduces fatty liver index and improves FibroScan score of patients with alcoholic fatty liver disease.
2. TRF normalises the liver enzyme profile of patients with alcoholic fatty liver disease.
3. TRF normalises the metabolic profile of the patients with alcoholic fatty liver disease.
4. TRF normalises the cytokines level and redox status of patients with alcoholic fatty liver disease.

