### **Biochemical assay**

Full blood count, liver profile (AST, ALT, GGT), lipid profile and fasting glucose test will be sent to an accredited laboratory for analysis using automated biochemistry analyser. HepatitisB and C status, as well as antibodies for autoimmune hepatitis will be assayed using an automated immunoassay machine. A portal of the blood will be centrifuged to isolate serum for acetyldehyde, malondialdehyde and inflammatory cytokines. These parameters will be assayed using enzyme-linked immunoassay based on manufacturer protocols.

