**DETAILED BUDGET**

Description	Price/unit (RM)	Unit	Total price (RM)
Research materials/ Consumables			
Tocovid SupraBio™ 200mg capsules: 6 months x RM 4 x 2 x 13 subjects	18720	1	18720
Placebo capsules: 6 months x RM 1 x 2 x 13 subjects	4680	1	4680
Multiplex immunoassay kits for biomarkers: 3 sampling points for all subjects (26 subjects)  Human Cytokines Profiling Selected Platform: M Sample type: Serum / Plasma  sCD40L, EGF, FGF-2, Flt-3 ligand, Fractalkine, G-CSF, GM-CSF, GRO, IFN- $\alpha$ 2, IFN- $\gamma$ , IL-1 $\alpha$ , IL-1 $\beta$ , IL-1ra, IL-2, IL-3, IL-4, IL-5, IL-6, IL-7, IL-8, IL-9, IL-10, IL-12 (p40), IL-12 (p70), IL-13, IL-15, IL-17A, IP-10, MCP-1, MCP-3, MDC (CCL22), MIP-1 $\alpha$ , MIP-1 $\beta$ , PDGF-AB/BB, RANTES, TGF- $\alpha$ , TNF- $\alpha$ , TNF- $\beta$ , VEGF, Eotaxin/CCL11, PDGF-AA	2160	26	56160
Immunoassay kits: 3 sampling points for all subjects (26 subjects).  6 kits x 3 sampling points (Each sample = RM 80)  Technical triplicate	1250	26	32500

Acetyldehyde, malondialdehyde, total antioxidant capacity, total superoxide dismutase, glutathione peroxidase, glutathione reductase			
HPLC Analysis: 3 sampling points for all subjects (26 subjects).  (RM 150 per Analysis)	450	26	11700
Plastics consumables - Blood tubes (heparin, EDTA, plain tubes), gloves, syringes and surgical mask, eppendorf tubes and tips 
 
• Cyrovials, 1.5 ml microcentrifuge tubes
 
• 15 ml and 50 ml centrifuge tube
 
• 10 ul, 100 ul, 200 ul and 1,000 ul pipette tips
 
	8000	1	8000
Cleaning consumables 
 
• Glove, hand soap, cleaning liquid, wipe, trash bag
 
	5000	1	5000
Stationary 
 
• All stationaries needed for the whole period of trial
 
• Photocopy of questionnaires, advertisements, case report forms and subject diaries
 
	2000	1	2000
Total			138760
Services			
Clinician Fee	200	26	5200
Phlebotomy: 5 sessions × 5 sampling points x 2 phlebotomists	5600	1	5600

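### Secondary outcomes: the direction rule is reversed for HDL-C, the cytokine matrix is plasma in one section and serum in another, and redox status has no listed outcome

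*Protocol*

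**What the plan says.** **Metabolic outcome.** Secondary Outcome Measures, item 2, lists five parameters together, ending with "high-density lipoprotein cholesterol (HDL-C), and triglycerides (TG); Unit: milligrams per deciliter (mg/dL". After the typical ranges, one sentence gives the direction for the whole list: "Higher values indicate worse metabolic profile". HDL-C is not excepted. Hypothesis 3 expects the metabolic profile to normalise on the study product.

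**Cytokine matrix.** Item 1 of the same section is "Change From Baseline in Plasma Cytokine Levels (Anti-inflammatory Effect of Tocotrienols) at baseline, 3 months, and 6 months", and its bullet repeats that IL-6, TNF-alpha and IL-1beta are measured in plasma. The Biochemical assay section says that a part of the blood "will be centrifuged to isolate serum for acetyldehyde, malondialdehyde and inflammatory cytokines". The multiplex kit line in the Detailed Budget has "Sample type: Serum / Plasma".

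**Redox.** Hypothesis 4 reads: "TRF normalises the cytokines level and redox status of patients with alcoholic fatty liver disease". Specific objective 4 covers the same ground, and the Abstract lists redox among the blood measurements. Biochemical assay and the Oxidative markers entry of the diagnostic algorithm name acetaldehyde and malondialdehyde. The Detailed Budget funds those two plus total antioxidant capacity, superoxide dismutase, glutathione peroxidase and glutathione reductase, at three sampling points for 26 subjects. Primary Outcome Measures covers liver enzymes, fatty liver index and liver stiffness. Secondary Outcome Measures covers cytokines and the metabolic profile. Neither lists a redox marker.

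**The concern.** The outcome definitions are where the protocol fixes what is measured, in what material, and which direction counts as benefit. Each of the three points fails at one of those tasks.

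- **Direction.** Read as written, a rise in HDL-C on the study product counts as worsening and a fall as improvement.
- **Matrix.** Plasma needs an anticoagulated tube and serum a plain one, and the budget buys heparin, EDTA and plain tubes. Staff processing a cytokine sample cannot follow both sections.
- **Redox.** Half of hypothesis 4 has no listed marker, unit, time point or direction. With several markers available, the choice of which one answers the hypothesis could be made after the results are seen.

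**Working it through.** The point is textual, so the main check sets the sections side by side.

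**1. Does it touch the plan's own figure?** The sample size rests on the fatty liver index: difference 12.82 − 3.86 = 8.96, SD 7.0, z-values 1.96 and 0.84.

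n = (1.96 + 0.84)² × 2 × 7.0² / 8.96² = 7.84 × 98 / 80.28 = 9.57, rounded up to 10 per group.

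With 20% loss, 10 / 0.8 = 12.5, rounded up to 13 per group and 26 in total. The stated figures are reproduced, and no input is a secondary outcome. Nothing below changes them.

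**2. Direction rule, component by component.**

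| Parameter | Rule as written | Usual reading | Agrees |
|---|---|---|---|
| Fasting glucose | higher is worse | higher is worse | yes |
| Total cholesterol | higher is worse | higher is worse | yes |
| LDL-C | higher is worse | higher is worse | yes |
| Triglycerides | higher is worse | higher is worse | yes |
| HDL-C | higher is worse | higher is better | **no** |

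One of five is reversed. The protocol's ranges do not rescue the rule. HDL-C is given as 40–60 mg/dL, but glucose and total cholesterol also have a lower limit above zero, so a range alone does not signal direction. The usual reading of HDL-C is general clinical knowledge; the protocol does not argue otherwise.

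**3. Does the rule enter a computation?** Statistical Analysis compares groups and times by mixed-design ANOVA, or by rank tests if the data are skewed. No composite, responder definition or one-sided test uses the direction. The HDL-C estimate, its sign and its p-value are the same under either rule. Only the interpretation changes.

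**4. Cytokine matrix.**

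| Section | Matrix |
|---|---|
| Secondary Outcome Measures, item 1 (title and bullet) | plasma |
| Biochemical assay | serum |
| Detailed Budget, multiplex kits | either |

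The first two contradict each other, and the third does not decide between them.

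**5. Redox coverage.**

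| Item | Cytokines | Redox |
|---|---|---|
| Objective 4 and hypothesis 4 | yes | yes |
| Planned assay (Biochemical assay) | yes | acetaldehyde, malondialdehyde |
| Budgeted at three sampling points | yes | those two plus four more |
| Listed outcome | yes, secondary item 1 | **none** |

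**6. What an open choice of marker could mean.** Statistical Analysis uses p < 0.05 and mentions Bonferroni only alongside the rank tests. As an illustration, assume six markers, one test each, and no true effect. If the markers were independent, the chance of at least one result below 0.05 would be 1 − 0.95⁶ = 0.26. If they were perfectly correlated, it would be 0.05. The documents give no correlations, so this range is an assumption and not an estimate for this trial.

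**The case against.** The strongest reply is that these are wording defects with little consequence. Much of it stands.

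- **HDL-C.** No analysis uses the direction sentence, and an investigator would probably read a routine lipid correctly anyway. A reader might infer that the metabolic analysis will produce a wrong result for HDL-C; the documents do not support that. What remains is that the wrong sentence is part of an outcome definition, where the reading is supposed to be fixed in advance.
- **Matrix.** A reader might infer that plasma and serum will be mixed across visits, adding noise or bias to change scores. No section plans this. If one matrix is used throughout, no such effect arises, and the budget line may only describe what the kit accepts. The contradiction between the two sections still needs settling.
- **Assay platform.** A reader might also see a conflict between a multiplex method and an enzyme-linked immunoassay. The outcome definition itself calls the method a multiplex ELISA, so the two descriptions are compatible and no platform conflict is shown.
- **Redox.** It would be too strong to say that redox is not measured or that hypothesis 4 cannot be answered. Assays are planned, and the cytokine half has an outcome. Nor are all six markers equally planned: four appear only in the budget. The gap is the absence of a listed redox outcome.
- **Choice of marker.** The protocol ranks no redox marker, so preferring malondialdehyde is a judgement and not something the text requires.

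**Conclusion.** The point holds as a set of outcome-definition errors that should be corrected. It does not threaten the trial's main result.

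- The direction rule is wrong for one of five metabolic components, in interpretation only.
- The cytokine matrix is contradictory for all three named cytokines. Whether this has any effect on the data is unknown.
- The redox half of objective 4 and hypothesis 4 has no listed outcome, while two markers are planned assays and six are budgeted at three time points.

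The sample size and primary outcomes are unaffected. The conclusion rests on the current text of the sections cited and on the usual clinical reading of HDL-C. It assumes nothing about how samples were in fact handled.

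**What to change.** 1. **Direction.** Replace the single sentence in Secondary Outcome Measures, item 2, with two statements: higher fasting glucose, total cholesterol, LDL-C and triglycerides are unfavourable; higher HDL-C is favourable. This is a wording change with no cost.

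2. **Matrix.** Name one matrix for cytokines, for all visits and participants, and use it in Secondary Outcome Measures, Biochemical assay and the budget line. Parts of the protocol describe recruitment and randomisation in the past tense, so samples may already exist. The choice must match what has been collected, and if that is not uniform it should be documented. The cost is one sentence if a single matrix has been used.

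3. **Redox.** Before unblinding, add one already-planned redox marker as a secondary outcome, with unit, time point and direction, compared between arms. Malondialdehyde is a reasonable choice: the Project Synopsis names it as the example of lipid oxidation, and the background on the investigational product reports reductions in earlier tocotrienol trials in non-alcoholic fatty liver disease. Label the other redox markers exploratory. This is a protocol amendment and not merely an edit, but for malondialdehyde it needs no new samples, visits or kits. The four markers that appear only in the budget should be added to Biochemical assay if they are to be run.
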